10.2.1 Resting State fcMRI

Brain imaging correlates of clinical pain have been notoriously difficult to measure;^{140,141} however, our previous publications provide consistent evidence that our resting state fcMRI approach assays the neurocircuitry contributing to chronic pain as well as its modulation by pharmacological and non-pharmacologic interventions.¹⁴²⁻¹⁴⁶ fcMRI is an adaptation of fMRI that examines intrinsic connectivity between brain regions - defined as ongoing synchronized neural activity occurring in the resting basal state. Intrinsic brain connectivity may be important for maintenance of synaptic connectivity and as such modulates the efficiency and extent of neuronal transmission between brain regions. Intrinsic connectivity, as measured by neuroimaging methods, follows known structural monosynaptic and polysynaptic pathways,^{147,148} likely reflecting meaningful neurophysiological activity¹⁴⁹ within known primary sensory, executive, and associative networks.¹⁵⁰ fcMRI investigations are conducted with participants in an awake state, simply resting in the scanner. These data can then be analyzed with techniques such as independent component analysis (ICA), seed-voxel connectivity, and graph theoretical network techniques. While multiple resting state networks have been shown to be altered in chronic pain states, we will focus on two cardinal networks: the default mode network (DMN), and the salience network (SLN). The DMN^{150,151} is a constellation of brain regions engaged in self-referential cognition, which are 'deactivated' during various externally focused tasks. Our group's data in FM have found increased connectivity between the DMN and insula, a brain region thought to integrate the multiple dimensions of pain.¹⁵² Greater clinical pain is correlated with greater DMN-insula connectivity¹⁴⁵, which is also diminished following treatment.^{143,144} The SLN, containing the insula, is largely activated when one's attention is focused on specific external or internal tasks.¹⁵³ This network is altered in centralized pain participants, primarily showing increased connectivity between the SLN and S1/M1.¹⁵⁴

Data Acquisition. Our group has published extensively using resting state connectivity outcomes in both cross-sectional participant-control^{144,155,156} and longitudinal treatment trials.¹⁴²⁻¹⁴⁴ In brief, participants will undergo two resting state fMRI scans; one will be at the beginning of the scanning session and the second will immediately follow the evoked low back pain maneuvers. Ten minutes of resting state fMRI data will be acquired using a T2*-weighted multiband echo planar imaging (EPI) sequence (TR/TE:720/33 ms, flip angle (FA) = 52°, matrix size 90x90 with 60 slices encompassing whole brain, field of view (FOV) = 180 mm x 208 mm, 2.0x2.0x2.0 mm voxels and 833 volumes, MB factor 8). During the resting state fMRI participants will be instructed not to focus on any particular task and stay awake with their eyes open and focused on a fixation cross. Since cardiac and respiratory fluctuations are known to influence brain connectivity,¹⁵⁷ these data will be collected simultaneously using a chest plethysmograph and infrared pulse oximeter. Only participant functional data of less than 2 mm of head motion inside the scanner will be included for analysis.

Preprocessing: fMRI data are preprocessed using fMRIprep (version 1.1.8)¹⁵⁸ running on the high-performance computing resources at our institution. Briefly, preprocessing steps include physiological noise removal (RETROICOR), motion correction, realignment, co-registration, normalization to standard MNI template, regression of nuisance variables (CompCor, motion parameters), and spatial smoothing (FWHM Gaussian kernel of 8mm).

Seed and Network (ICA) Connectivity Analysis. Seed to whole brain functional connectivity analysis is performed using the Conn (Cognitive and affective neuroscience laboratory, MIT, Cambridge, USA) functional connectivity toolbox. Seed regions (5 mm spheres) are chosen based on previously published fMRI studies of chronic pain, including: the insula,¹⁴⁶ and S1/M1.^{154,159} Network seeds (DMN and SLN) will be derived from ICA, as previously published.^{144,145,160} White matter, CSF, and motion parameters are used as covariates of no interest. Data is band pass filtered (0.01-0.1Hz) to remove linear drifts and high frequency noise from the data. First level analysis will correlate the time course from the seed/network to all brain voxels creating connectivity maps for each seed or network.

Group Level Analysis. Seed and network-to-whole-brain connectivity maps will be entered into a multiple regression model in SPM with change in pain interference (post minus pre-treatment) as a covariate of interest. Age and sex will be entered as covariates of no interest. Although not the primary objective of Aim 3, we will also conduct exploratory analyses to examine the mechanism of action of specific treatments. Changes in connectivity patterns following each of the phase 1 treatments will be performed using paired sample t-tests in SPM12. Resulting maps are thresholded at $p < .001$ uncorrected voxel threshold with $p \leq .05$ FDR significance corrected for multiple comparisons.

Graph Theory Analyses. Using Graph Theory Analyses the brain is defined as a network of 264 non-overlapping nodes (10 mm spheres) connected by edges or links.^{161,162} These nodes and the preprocessed fMRI data are entered into the Conn functional connectivity toolbox to create Fisher z-transformed bivariate correlation (Pearson's r) matrices (264 x 264) for each participant. To exclude weak or spurious connections, matrices are thresholded beginning with the strongest 5% connections and proceeding in steps of 5% up to 40% density, resulting in binary undirected graphs containing the most significant edges. Using the Brain Connectivity Toolbox,¹⁶³ we will calculate the following graph theoretical measures to assess global (efficiency, modularity, rich-club) and nodal (hub status) network properties, as previously published.¹⁶⁴ To assess hub status, we will calculate eigenvector centrality which takes into account the connectedness of a node, in addition to the connectedness of that node's neighbors. Hub status will be assigned to a node if the eigenvector centrality is greater than one standard deviation above the group mean.^{165,166}

Group Level Analysis. We will determine if hub status and rich club organization predicts treatment response. Individual hub measures will be entered into regression analyses to predict ($p < .05$) association with change in pain interference pre- versus post-treatment.

Machine-learning based prediction analyses: SVM analyses will be performed for the previously mentioned modalities using the libsvm toolbox version 3.18¹⁶⁷ in Matlab 2017a and using group level images from the previously described modalities. Participant images will be labeled as a responder or non-responder based on change score of pain interference pre- versus post-treatment using a cutoff of a 30% reduction or a median split. SVM classification will be performed using a linear kernel with k-fold cross-validation to calculate classification accuracies. SVM model weights will be averaged across all cross-validation cases to investigate spatial distribution of the weights, with label permutation (n = X*1000) to establish significance levels.

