18.1.5 Descriptive statistics

We will use descriptive statistics to assess data quality and characterize relationships between phenotype features prior to each treatment. In preparation for the main multivariate model-based analysis we will look at correlations between phenotype variables and responses with correlation analysis and scatterplots, analyze data for evidence of (near) collinearity between factors, study patterns of missing data, and conduct univariate analysis using models described below. The goal of this analysis is to elicit a good feel for the specific data in our team of analysts and to guide an initial approach to data reduction and predictive model trimming. Another round of descriptive model-based analysis will occur after the multivariate model-based data analysis to assess the adequacy of proposed models with model diagnostic plots and other tools.

Longitudinal data analysis. For hypothesis testing, we will use model-based likelihood ratio tests. The main hypotheses of differential treatment effects (treatment moderators, treatment effect modifiers) will be handled by introduction of the interaction terms between the phenotype and treatment indicator variables. We will base longitudinal analysis on multivariate linear and logistic mixed models with choice appropriate to the type of response variable (Logistic regression with yes/no type variables; the Proportional Odds Cumulative Logit for modeling ordinal responses; linear model and generalized linear model with continuous quantitative scores). Gaussian subject-specific intercept term will be used to model the effect of unmeasured factors shared by longitudinal observations on the same subject. While the continuous form of analgesic and secondary endpoint variables will be used in the primary line of analysis, for robustness and to gain insight into a need for specific link functions and variable transformations, we will also use binary (clinically relevant 30% and 50% improvement in analgesic responses [yes/no]) as well as ordinal form of the responses.

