Power for prediction. We expect that at least 30% of patients will show 50% improvements in analgesic outcomes under each of the treatments. We expect the predictive panel of light phenotypic variables to show AUC exceeding a clinically relevant AUC of 0.7, dependent on the specific setting. Under this assumption we will have the power of at least 91% to reject the null hypothesis AUC of 0.5 by a two-sided test in the subgroup analysis setting described above. With the panel including the deep phenotyping variables we expect to be able to reach a better AUC of 0.8 or higher. However, the analysis is based on smaller size of the subgroup (40 vs. 100). This results in the power of at least 89% for a similar test of AUC.

Go/no-go decisions to recommend model-based predictor panel for future clinical use. We are targeting a high sensitivity of the predictive panel of 80%. Under this scenario, the cross-validated ROC curve will be kernel-smoothed, and the decision threshold will be determined from the smoothed data to meet the 80% sensitivity. Under a normal approximation to the panel score distribution for patients who show 50% improvement and the ones who do not, in the hypothetical scenario of the above power calculation, we assess that the expected specificity value at 80% sensitivity will be around 50%. To provide guidance at the end of the study as to whether the panel is worth recommending for use in the clinical setting, worth a further study or non-promising, we will consider the overall rate of correct decisions. With the targeted sensitivity and specificity and the expected pain improvement rate in the subgroup, we are expecting that the decision will be at least 41%

correct overall. We will consider the assay not useful if it has the true overall correct decision rate of 25% or less. Dependent on the outcome, the panel will be potentially considered worth of further pursuit in the sense of potentially doubling the sample size in a future study and having a non-ambiguous decision at the end with Type I and type II errors of 5% each. Using the Fleming sequential testing design we conclude that with less than 13 correct predictions of improvement under treatment at the end of the current study the panel will be considered not worth pursuing. With 21 or more correct decisions, the biomarker will be considered clinically relevant, and with the number of correct decisions between 13 and 21, we will consider the biomarker worth of further study.

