## 4.3 Endpoints

The primary study endpoint is the change in the PROMIS (Patient-Reported Outcomes Measurement Information System) pain interference score between the T2 pre-intervention visit and T3 post-intervention visit. The PROMIS pain interference measures the degree to which a patient's pain interferes with the patient's life. The survey questions assess interference in different domains including work around the home, recreational activities, and social activities. A univariate pain interference score is calculated from the respondent's answers. This process is described in Section 9.2.

The study's secondary endpoints consist of the change in the Pain Intensity (PEG) and the Patient Global Impression of Change (PGIC) between the T2 pre-intervention visit and T3 post-intervention visit. The other exploratory PROMIS measures will include a measure of physical functioning, fatigue, sleep disturbances, and cognition. The process of computing each secondary endpoint from survey responses is found in Section 9.2.

Figure 1 Study aims and overview

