#### **5.4.2 Inclusion Criteria for Light Phenotyping**

- We will use the definition of chronic low back pain (cLBP) described in the NIH Task Force Report on Research Standards for Chronic Low Back Pain, i.e. low back pain present at least six months, and present more than half of those days.
- Individuals must have a pain interference score of  $\geq 60$  on PROMIS Pain Interference at T1 for inclusion. The normal population mean and standard deviation for the PROMIS Pain Interference measures are 50 and 10 points, respectively. Therefore, participants must be 1 SD above the population mean ( $>=60$ ) for inclusion.
- Individuals must be willing and eligible to be randomized to receive at least three of the four proposed treatments.

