## **8.2 Derived variables**

The study's primary and secondary endpoints are each scored as recommended by instrument authors. The PROMIS-based measures will be derived in Qualtrics using a tool released by HealthMeasures.net. The PROMIS composite scores have a population mean and standard deviation equal to 50 and 10 points, respectively. The Oswestry Disability Index is calculated by summing the individual item scores (values ranging from 0 – 5) and multiplying by 2. Its range runs from 0 to 100.

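### A 30% fall is used as a responder cutoff on a PROMIS T-score, where a percentage has no fixed meaning; the alternative label is left open, and the scale for the other percentage rules is not named

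*Protocol*

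**What the plan says.** Protocol 10.2.1, in the machine-learning paragraph, labels each participant a responder or non-responder "based on change score of pain interference pre- versus post-treatment using a cutoff of a 30% reduction or a median split". Protocol 10.2.3 refers back to that section for the SVM on evoked-pain images.

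The outcome is PROMIS Pain Interference (Protocol 1.1, SAP 4.3). SAP 5.4.2 gives its metric: "The normal population mean and standard deviation for the PROMIS Pain Interference measures are 50 and 10 points, respectively". SAP 8.2 says the same of the PROMIS composite scores generally. Entry requires a score of at least 60, which SAP 5.4.2 places at T1; the endpoint is the change from T2 to T3.

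Protocol 18.1.5 adds binary responses defined by "clinically relevant 30% and 50% improvement in analgesic responses", as a robustness form. Its power-for-prediction paragraph says: "We expect that at least 30% of patients will show 50% improvements in analgesic outcomes under each of the treatments". On that premise it states power of at least 91% (AUC 0.7, 100 patients) and at least 89% (AUC 0.8, 40 patients). The go/no-go rule that follows classifies patients by the same 50% improvement. Neither paragraph names the instrument to which the percentages apply.

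**The concern.** On a scale where 50 is the population average, zero does not mean absence of interference, so a percentage fall is not a proportion of the problem removed. The cutoff also asks for more points from patients who start worse: 18 points from 60, 21 from 70.

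Two things are at stake. First, if few patients meet the 30% cutoff, a classifier trained on that label has little to learn from. The plan would then be left with the median split, taken up once the class sizes are known. Label permutation under the label finally used does not account for a choice made between two labels. Second, if the percentages in Protocol 18.1.5 are also meant for the T-score, the responder share assumed for the AUC power and the go/no-go rule would be far out of reach.

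**Working it through.** **1. The plan's own power figures.** Inputs from Protocol 18.1.5: 30% responders, so 30 of 100 and 12 of 40; AUC 0.7 and 0.8 against 0.5; two-sided test, with the 5% level taken from the correlation test in the same section. The Hanley-McNeil variance is [A(1-A) + (n1-1)(A/(2-A) - A²) + (n0-1)(2A²/(1+A) - A²)] / (n1·n0), and power is Φ((A - 0.5 - 1.96·SE0)/SE1).

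- 30:70, A = 0.7: SE0 = 0.0633, SE1 = 0.0601; Φ((0.2 - 0.1241)/0.0601) = 89.7%.
- 12:28, A = 0.8: SE0 = 0.1008, SE1 = 0.0840; Φ((0.3 - 0.1976)/0.0840) = 88.8%.

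A simulated Mann-Whitney test gives 91.1% and 90.1%. The stated 91% and 89% therefore reproduce within about two points, given 30% responders.

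**2. What the cutoffs mean on the T-score.** This uses only figures in the documents.

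| Starting score | 30% fall | Ends at | 50% fall | Ends at |
|---|---|---|---|---|
| 55 | 16.5 | 38.5 | 27.5 | 27.5 |
| 60 | 18 | 42 | 30 | 30 |
| 65 | 19.5 | 45.5 | 32.5 | 32.5 |
| 70 | 21 | 49 | 35 | 35 |

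From 60, the 30% rule ends 0.8 SD better than the population mean and the 50% rule 2 SD better.

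**3. Share of patients meeting the cutoffs.** This needs the mean fall m and the SD s of change, which the documents do not give. Assumed: m = 3-10 points, s = 5-10, baseline b = 60-65, normal change. The share is Φ((m - p·b)/s), with p = 0.3 or 0.5.

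- 30% cutoff, lowest (b = 65, m = 3, s = 5): Φ(-16.5/5) = Φ(-3.3) = 0.05%.
- 30% cutoff, middle (m = 5, s = 7): Φ(-13/7) = 3.2% from 60 and Φ(-14.5/7) = 1.9% from 65. That is about 3-5 of the 160 deep-phenotyped patients, or about 1 of 40.
- 30% cutoff, highest (b = 60, m = 10, s = 10): Φ(-0.8) = 21%, about 34 of 160.
- 50% cutoff, highest (same case): Φ(-20/10) = 2.3%.

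Because the threshold of 60 applies at T1, T2 scores can be lower. From 55, the 30% share is Φ((5 - 16.5)/7) = 5.0% in the middle case and Φ((10 - 16.5)/10) = 26% in the most favourable. The 50% share is then at most Φ((10 - 27.5)/10) = 4.0%.

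**4. Median split.** By construction, about 80 of 160 per class, or 20 of 40 within an arm.

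**5. If the 50% rule in Protocol 18.1.5 refers to the T-score.** For 30% of patients to fall by half, the mean fall would have to be 0.5b - 0.524s. That is 24.8 points for b = 60, s = 10 and 29.9 points for b = 65, s = 5. With the formula in step 1, 2 or 3 responders of 100 give power of about 16% or 22%, against the stated 91%. With 1 or 2 of 40 the power is about 15% or 27%, against 89%. The normal approximation is rough at such counts, so these figures are indicative.

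**The case against.** The strongest reply has four parts.

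- **The same sentence allows a median split.** A reader might infer that the SVM analyses are bound to have almost empty classes. The text does not support that, because one of its two permitted labels is balanced. What remains is that the plan gives no rule for choosing between the two labels. It does not provide for choosing after the data are seen either; that risk comes from the gap.
- **The share meeting 30% depends on inputs that are not in the documents.** A reader might infer that almost nobody can reach the cutoff. The assumed range runs up to 21%, and higher for T2 scores below 60, so only a probably small class can be claimed.
- **The 50% rule is attached to analgesic outcomes, not to pain interference.** The schedule of activities includes several pain-intensity measures, and the opening of Protocol 18 lists functional outcomes apart from analgesic responses. A pain-intensity reading is therefore open. On the other side, Protocol 18.2.2 names PROMIS Pain Interference as the primary treatment outcome, and SAP 6.1 makes its change the primary measure of within-patient improvement. Neither reading is established; for these paragraphs the defect shown is an unnamed scale.
- **These analyses are secondary.** Protocol 18.1.5 says: "While the continuous form of analgesic and secondary endpoint variables will be used in the primary line of analysis". SAP Objectives 1-3 model the score itself and define no percentage responder, and SAP 6.1 does not carry the AUC power forward. This stands in full and limits the severity.

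**Conclusion.** The point holds in a limited form. The 30% cutoff in Protocol 10.2.1 suits the T-score poorly, and that conclusion needs no outside input: from 60 it demands an 18-point, 1.8 SD fall to better than the population mean. How many patients meet it is uncertain: about 0.05% to 21% under the assumed changes from baselines of 60-65, and 2-3% at mean 5 and SD 7. The median split avoids small classes but is a different label, with no rule for when it applies.

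For Protocol 18.1.5 the conclusion is conditional. If the percentages refer to the T-score, at most about 2% would show a 50% fall under the same assumptions, and the 30% premise behind the 91% and 89% powers and the go/no-go rule fails. If they refer to a pain-intensity scale, this calculation says nothing against that premise. A reader might take the finding to reach the primary endpoint; it does not. It should be corrected, but it does not threaten the main result.

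**What to change.** In Protocol 10.2.1, and so in 10.2.3, define response on pain interference by one rule chosen now: either a fixed fall in T-score points, with the number stated and justified by the study team, or the median split alone, saying whether it is taken within arm or pooled. Keep the 30% and 50% rules for 0-10 pain-intensity scales. In Protocol 18.1.5, name the scale to which the 30% and 50% improvements and the expected 30% responder share apply. If it is the T-score, restate the AUC power and the go/no-go figures with a responder share that can be supported. Protocol 10.3 compares gene expression between responders and non-responders without defining them and should point to the same definition.

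The cost is protocol wording and, in the T-score case, one recalculation. No data collection changes. The SAP has no percentage rule to correct; it needs a matching sentence only if these analyses are to be run under it.

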10.2.2 Proton Magnetic Resonance Spectroscopy (1H-MRS)

During ¹H-MRS, quantifiable measures of brain metabolites will be acquired from multiple brain regions non-invasively. The metabolite we will focus on is glutamate, the brain's major excitatory neurotransmitter. Previous ¹H-MRS studies, performed by our group, have examined changes in Glx (combined glutamate and glutamine) in cross sectional participant-control^{103,136,168,169} and longitudinal treatment studies.^{104,143} We find that FM participants display elevated Glx within the posterior insula and this concentration is reduced following active treatment, and this reduction was correlated with a reduction in clinical pain.¹⁴³ We have also shown that pelvic pain participants have elevated Glx within the anterior insula which is in turn associated with increased connectivity to the medial prefrontal cortex, a DMN structure.¹⁷⁰

Data Acquisition: ¹H-MRS will be performed as in our previously published studies.^{103,143,170} In brief, we will examine Glx within the posterior insula twice (before and after back pain maneuvers). Our primary ¹H-MRS outcome will be baseline Glx within the posterior insula. ¹H-MRS studies are performed on the same magnet as fMRI. PRESS (TR/TE=2000/35 ms) single voxel ¹H-MRS is performed on the region of interest with voxel sizes of 2x2x3 cm. The water signal is recorded using 8 averages. Standardized voxel placements are guided by visual inspection of anatomical T1-weighted images as reported previously.¹⁰³

Preprocessing: Raw data from each single-voxel MR spectroscopy sequence will undergo manual post-processing using ¹H-MRS software (LCModel; Stephen Provencher, Oakville, Ontario, Canada). LCModel uses a linear combination of individual spectra obtained from pure molecular species to fit the experimental spectra.¹⁷¹ Glx values will be calculated both as an absolute concentration using the water signal for normalization and as a ratio to creatine. Glx absolute concentrations will be reported in arbitrary institutional units. Correction for cerebral spinal fluid (CSF) volume, which can dilute ¹H-MRS-derived Glx values, will be performed as reported previously.¹⁰³ Metabolite concentrations will be excluded if the Cramér-Rao bounds are greater than 20%.

Group Level Analysis: CSF-corrected Glx values will be entered into a multiple regression model in SPSS with change in pain (post minus pre-treatment) as the dependent variable and Glx values as a covariate of interest. Age and sex will be entered as nuisance regressors.

10.2.3 fMRI of Evoked Cuff Gastrocnemius Pain

Whole brain blood oxygen level-dependent (BOLD) functional images will be acquired using the same 3 Tesla scanner and T2*-weighted EPI multiband sequence as described for the resting state scan. Each participant will undergo a 11-minute block design scan, during which 6 cuff pressures (equal pressure = 15-30 and 100-115 mmHg; equal pain = 40-60/100 numerical rating scale (NRS) units will be applied to the left calf using the pressure cuff device (described in Section 10.1) in pseudo-random order. Pain levels for each participant will be determined during the QST assessment. Each pressure stimulus will be applied for 14 seconds. Prior to each pressure stimulus, a 4-second visual cue will be presented to signal upcoming cuff pressure to limit any stimulus-onset startle reflex. Participants' head motion will be minimized using foam pads around the head, and a strap secured across the forehead.

Pre-processing: Same as resting state fcMRI. See Section 10.2.1.

Group level analysis: The activation maps (pain minus rest) will be entered into a GLM to determine the neurobiological correlates of evoked pain that best predict treatment response (change in pain as the dependent variable). In addition, SVM will be implemented to create a machine learning model for prediction and discrimination between responder and non-responder (see corresponding Section 10.2.1). Resulting maps are thresholded at $p < .001$ uncorrected voxel threshold with $p \leq .05$ FDR significance corrected for multiple comparisons.

Physical Maneuvers to Evoke Back Pain. During their initial in-clinic visit, participants will perform simple exercise-like maneuvers (e.g., arching/bending the back to elicit lumbar flexion/extension) to evoke temporary increases in back pain. The experimenter will measure the degree to which a participant must flex or extend their back to evoke a clinical pain increase of at least 30% over their baseline. Detailed records will be taken of frequency and duration required to achieve the targeted clinical pain level to ensure the same maneuvers are performed at subsequent fMRI visits. For each participant, individualized physical maneuvers that are most reliable in exacerbating clinical pain will be picked for the fMRI sessions. During fMRI, participants will undergo baseline functional imaging (capturing brain activity at their baseline pain level), followed by a short (15-20 minute) break whereby participants will perform the physical maneuvers outside the scanner. Participants will re-enter the MRI environment and undergo post-exacerbation functional imaging (at their elevated pain level). Imaging analyses will focus on changes in brain activity within an individual (from baseline to exacerbated back pain). Participants will be cautioned to not increase their pain to a level that they are unable to tolerate. This procedure to exacerbate clinical back pain levels has been well-tolerated, feasible, and extensively used in past research,¹⁷²⁻¹⁷⁴ however participants that are uncomfortable or concerned about performing this task can choose to skip it and complete the remainder of the fMRI session.

Autonomic Nervous System (ANS) acquisition during fMRI. During each fMRI scan, electrocardiogram (ECG), photoplethysmogram (PPG), respiration, skin temperature, and GSR data will be collected at 500 Hz using an MRI-compatible, noninvasive BIOPAC MP160 System (BIOPAC Systems, Goleta, CA, USA). For the ANS outcomes, ECG and respiratory volume signals will be acquired with 2 MR-compatible Ag/Ag-Cl transcutaneous sensors placed above and below the heart and a pneumatic belt placed just below the rib cage. GSR, PPG and temperature will be acquired using MR-compatible Ag/Ag-Cl transcutaneous sensors placed on the fingertips of the index and middle fingers.

Analysis: Inter-beat-intervals (segmented into 5-minute windows) and GSR signals (15-second epochs) will be imported into MATLAB for feature extraction. Windows with >15% missing data will be excluded. HRV features, including all time- and frequency-domain and Kubios features,¹⁷⁵ and tonic and phasic GSR features,¹⁷⁶ will be extracted using MATLAB. After feature extraction, we will utilize a semi-supervised machine learning paradigm¹⁷⁷ to combine the continuous HRV and GSR signals and characterize vagal tone.

Feasibility. We have previously collected ANS activity in participants undergoing QST and neuroimaging without difficulty. Risks associated with these measures are minimal since they are non-invasive. However, some participants may experience anxiety and/or a general unease associated with unfamiliar physiological testing and/or when applying or removing sensors. Participants will be instructed that they may stop participating at any time.

